## 4. ANALYSIS SETS (POPULATIONS FOR ANALYSIS)

Data for all subjects will be assessed to determine if subjects meet the criteria for inclusion in each analysis population prior to releasing the database and classifications will be documented per standard operating procedures.

| Population   | Description  |
|--|--|
| Modified Intention to Treat (mITT) or Full Analysis Set (FAS) | All participants randomly assigned to IP and who apply at least 1 dose of IP.   |
| CCI  |  |
| Safety Analysis Set   | All participants randomly assigned to IP and who apply at least 1 dose of IP. Participants will be analyzed according to the product they actually have received. |

## 5. GENERAL METHODOLOGY AND CONVENTIONS

The primary analysis will be performed when all randomized subjects have either completed their 6-week study participation period or withdrawn early or should the study be stopped prematurely due to any reason, and the database is released.

### 5.1. Hypotheses and Decision Rules

Statistical inference will be made on the primary endpoints: (percentage change from baseline in EASI score at Week 6 and change from baseline in PASI score at Week 6). The null hypothesis is that there is no difference PF-07038124 its corresponding vehicle arm (ie, AD vehicle and Psoriasis vehicle). The alternative hypothesis is that the PF-07038124 arm being tested is superior to its

corresponding vehicle at Week 6 in AD and/or Psoriasis patients. The study will be considered positive for AD and/or Psoriasis, if either one or both null hypotheses are rejected.

*The sample size calculation is based on the primary endpoint (percentage change from baseline in EASI score at Week 6). A total of 56 randomized participants in 1 treatment group and 1 vehicle group (28/arm) will provide approximately 90% power to detect a difference of 50 in percentage change from baseline with a common standard deviation 48% between PF-07038124 and a vehicle arm, controlling the two-sided error rate alpha 0.05. These calculations allow for a 25% dropout rate leaving 42 evaluable participants (21/arm).*

*For the key secondary endpoint, IGA response rate of clear or almost clear and  $\geq 2$  points improvement at Week 6, assuming 20% rate for vehicle and 55% rate for the treatment, this sample size provides 66% power controlling the two-sided error rate alpha 0.05.*

*The sample size is based on the primary efficacy endpoint, PASI change from baseline at Week 6. With an assumed standard deviation of 4.2 and treatment difference of 4.5, a total of 32 randomized participants in 2 treatment groups (16/arm) will provide approximately 80% power for the comparison of active versus vehicle group at a two-sided significance of 0.1. This calculation allows for an approximate 25% dropout rate, that is 12 participants evaluable per arm at Week 6, where evaluable is defined as included in the mITT set.*

*For the key secondary endpoint, PGA response rate of clear or almost clear and  $\geq 2$  points improvement at Week 6, assuming 20% rate for vehicle and 65% rate for the treatment, this sample size provides 61.9% power controlling the two-sided error rate alpha 0.05.*

## **5.2. General Methods**

### **5.2.1. Analyses for Binary Endpoints**

Landmark (cross-sectional) analyses of key binary endpoints will be analyzed by first treating missing data as non-responders and then applying Chan and Zhang's exact confidence interval (CI) method.

For all binary endpoints, a summary based on the mITT of the number of subjects in each category based on observed cases in each treatment arm at each time point will be produced and the response rate will also be plotted against time, by treatment group.

CCI

### **5.2.2. Analyses for Continuous Endpoints**

Landmark (cross-sectional) analysis of key continuous endpoints will use analysis of covariance (ANCOVA). The ANCOVA model will include terms for treatment arm and baseline score of the dependent variable. Least-squares means at the mean overall baseline score will be presented along with 90% confidence intervals.

Mixed model repeated measures (MMRM) models will be used. The fixed effects of treatment, visit, and treatment by visit interaction will be included. Visit will be modeled as a categorical covariate. Unstructured covariance matrix will be assumed for the model errors. Compound symmetry covariance matrix will be used if the model with unstructured covariance doesn't converge.

When modeling the change from baseline values, the variable for visit will start with the first post-baseline visit, and the actual baseline value will be included as a covariate. At each visit, estimates of least square mean (LSM) values and the LSM differences between the PF-07038124 treated group and the corresponding vehicle group will be derived from the model for AD and Psoriasis patients separately. The corresponding p-values and 90% confidence intervals will also be derived from the model.

Unless stated otherwise, descriptive summary statistics for all continuous variables will be presented on mITT observed data by treatment group and will include n, mean, median, standard deviation, minimum and maximum.

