4. STUDY DESIGN

4.1. Overall Design

This is a phase 2a, randomized, double blind, vehicle controlled, parallel group, multicenter study on the efficacy, safety, tolerability and PK of PF-07038124 0.01% QD versus vehicle control in the treatment of adult participants with mild to moderate AD or mild to moderate plaque psoriasis. In this study the efficacy of PF-07038124 ointment versus vehicle will be assessed in two different indications – there is a separate vehicle control group for each indication.

A total of approximately 88 participants with AD or psoriasis will be randomly assigned to study intervention in this basket trial design.

For AD, a maximum of approximately 56 participants will be randomly assigned to study intervention such that approximately 42 evaluable participants complete the study. Assuming a 25% drop out rate, approximately 28 participants will be randomized to either PF-07038124 or vehicle control to achieve approximately 21 completers in each group. Randomization will be stratified by baseline disease severity (mild [Investigator's Global Assessment or IGA = 2] vs. moderate [IGA = 3]). Up to 25% of AD participants will have an IGA score of 2 at baseline.

For psoriasis, a maximum of approximately 32 participants will be randomly assigned to study intervention such that approximately 24 evaluable participants complete the study. Assuming a 25% drop out rate, approximately 16 participants will be randomized to PF-07038124 or vehicle control to achieve 12 completers in each group. Randomization will be stratified by baseline disease severity (mild [Physician Global Assessment or PGA = 2] vs. moderate [PGA = 3]). Up to 25% of participants will have a PGA score of 2 at baseline.

The total duration of study participation will be approximately 17 weeks, including a screening period of up to 6 weeks, a double-blind, placebo-controlled treatment period of 6 weeks, and a safety follow-up period of 4-5 weeks from last dose of study drug to last study visit. The study intervention arms and duration for AD and psoriasis participants are the same (See [Section 1.1](#) for detailed Study Intervention Groups and [Section 1.2](#) for Study Schema).

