9. STATISTICAL CONSIDERATIONS

Detailed methodology for summary and statistical analyses of the data collected in this study is outlined here and further detailed in a SAP, which will be maintained by the sponsor. The SAP may modify what is outlined in the protocol where appropriate; however, any major modifications of the primary endpoint definitions or their analyses will also be reflected in a protocol amendment.

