9.4.1. Efficacy Analyses for AD

Endpoint	Statistical Analysis Methods
Primary: Percent Change from Baseline EASI at Week 6	A landmark analysis using analysis of covariance of percent change from baseline in EASI, adjusting for the baseline EASI score, to estimate the effect of the initially randomized treatment in the absence of prohibited medication regardless of treatment compliance. The analysis will use the mITT analysis set. Missing data due to any cause including censoring due to initiation of prohibited medication will be imputed using the corresponding vehicle arm, missing data in a vehicle arm will be imputed using data from the vehicle arm assuming data are missing at random (MAR). The analysis will combine the results from the multiple imputations using Rubin's rule as implemented in SAS PROC MIANALYZE.
Secondary: IGA Response at Week 6	A landmark analysis of the composite endpoint; achieving IGA without prohibited medication, while remaining on study and providing data. The analysis will use the mITT analysis set. Based on the definition of the composite endpoint all participants in the mITT set will have a response for all visits (ie, there is no missing data). The proportions responding and

Endpoint	Statistical Analysis Methods
	the corresponding risk difference comparing active treatment arm to vehicle group will be analyzed using the unconditional exact method; the risk differences and the corresponding 2-sided unconditional exact 90% confidence intervals will be computed using Chan and Zhang (1999) ¹⁶ method.

CCI

Other continuous secondary endpoints at time points specified in the SoA including change from baseline EASI, will be analyzed as described for the primary estimand along with descriptive statistics and possibly graphical displays.

Other binary secondary endpoints at time points specified in the SoA including, CCI EASI 75, CCI IGA of clear or almost clear will be analyzed as described for the secondary estimand along with descriptive statistics and possibly graphical displays.

CCI

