9.4.2. Efficacy Analyses for Psoriasis

Endpoint	Statistical Analysis Methods
Primary: Change from Baseline PASI at Week 6	A landmark analysis using analysis of covariance of change from baseline PASI, adjusting for the baseline PASI score, to estimate the effect of the initially randomized treatment in the absence of prohibited medication regardless of treatment compliance. The analysis will use the mITT analysis set. Missing data due to any cause including censoring due to initiation of prohibited medication will be imputed using the corresponding vehicle arm, missing data in a vehicle arm will be imputed using data from the vehicle arm assuming data are missing at random (MAR). The analysis will combine the results from the multiple imputations using Rubin's rule as implemented in SAS PROC MIANALYZE.
Secondary: PGA Response at Week 6	A landmark analysis of the composite endpoint; achieving a PGA response (a score of clear (0) or almost clear (1) and ≥ 2 point improvement from baseline) without prohibited medication, while remaining on study and providing data. The analysis will use the mITT analysis set. Based on the definition of the composite endpoint all participants in the mITT set will have a response for all visits (ie, there is no missing data). The proportions responding and the risk difference between treated arms and their corresponding vehicle control arm will be analyzed using an unconditional exact method: risk differences and corresponding 2-sided unconditional exact 90% confidence intervals will be computed using the

Endpoint	Statistical Analysis Methods
	Chan and Zhang (1999) ¹⁶ method.

CCI

Other continuous secondary endpoints at time points specified in the SoA including: absolute PASI, change from baseline PASI, percent change from baseline PASI, absolute and change from baseline Itch Severity Score, absolute and change from baseline Psoriasis Symptom Inventory will be analyzed as described for the primary estimand along with descriptive statistics and possibly graphical displays.

Other binary secondary endpoints at time points specified in the SoA including, CCI PASI 75, CCI PGA of clear or almost clear will be analyzed as described for the secondary estimand along with descriptive statistics and possibly graphical displays.

CCI

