## 2.2. Study Design

*This is a phase 2a, randomized, double blind, vehicle controlled, parallel group, multicenter study on the efficacy, safety, tolerability and PK of PF-07038124 0.01% QD versus vehicle control in the treatment of adult participants with mild to moderate AD or mild to moderate plaque psoriasis. In this study the efficacy of PF-07038124 ointment versus vehicle will be assessed in two different indications – there is a separate vehicle control group for each indication.*

[figure not shown]
*A total of approximately 88 participants with AD or psoriasis will be randomly assigned to study intervention in this basket trial design.*

*For AD, a maximum of approximately 56 participants will be randomly assigned to study intervention such that approximately 42 evaluable participants complete the study. Assuming a 25% drop out rate, approximately 28 participants will be randomized to either PF-07038124 or vehicle control to achieve approximately 21 completers in each group. Randomization will be stratified by baseline disease severity (mild [Investigator's Global Assessment or IGA = 2] vs. moderate [IGA = 3]). Up to 25% of AD participants will have an IGA score of 2 at baseline.*

*For psoriasis, a maximum of approximately 32 participants will be randomly assigned to study intervention such that approximately 24 evaluable participants complete the study. Assuming a 25% drop out rate, approximately 16 participants will be randomized to PF-07038124 or vehicle control to achieve 12 completers in each group. Randomization will be stratified by baseline disease severity (mild [Physician Global Assessment or PGA = 2] vs. moderate [PGA = 3]). Up to 25% of participants will have a PGA score of 2 at baseline.*

*The total duration of study participation will be approximately 17 weeks, including a screening period of up to 6 weeks, a double-blind, placebo-controlled treatment period of 6 weeks, and a safety follow-up period of 4-5 weeks from last dose of study drug to last study visit. The study intervention arms and duration for AD and psoriasis participants are the same.*

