## **5.3. Methods to Manage Missing Data**

### **5.3.1. Efficacy Data**

The primary analysis will use the primary estimand continuous endpoint set. For each landmark analysis (eg, cross sectional analysis by week) missing data, except missing due to COVID-19 pandemic, will be imputed using a control based imputation method. PROC

MI will first be called at the visit and a control based method (implemented with the MNAR option) will impute missing vehicle observations under the assumption data are missing at random (MAR) and impute missing treatment observations assuming they are similar to corresponding vehicle patients.

Summaries of continuous data will use the observed data only and no additional considerations are needed.

Analysis of binary data will use the Secondary Estimand Categorical Endpoint Set. This dataset by definition has no missing data since all missing values, except missing due to COVID-19 pandemic, will have been set to a non-responder. Summaries will use the Observed Efficacy Set and will report results on an observed case (OC) basis.

If a subject misses a visit due to COVID-19, he/she will be excluded from the analysis for that visit; If a subject discontinues treatment or withdraws from the study due to COVID-19, he/she will be excluded from the analyses after the treatment discontinuation visit or study withdrawal visit, respectively.

CCI

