##### 6.1.1.1. Main Analysis

- Estimand strategy: Primary Estimand ([Section 2.1.1](#)). This estimand is intended to provide an estimate of the treatment effect in the absence of prohibited medication use in a population that may or may not be fully compliant with the treatment.
- Analysis set: mITT ([Section 4](#)) using data prepared in the description of the full analysis set.
- Analysis methodology: Percent change from baseline will be analyzed using an ANCOVA with the observed (or imputed) Week 6 change from baseline EASI score as the dependent variable with treatment arm and baseline EASI score as the independent variables. Same method will be used for change from baseline PASI score at Week 6.
- Intercurrent events and missing data: Data prohibited medication will be excluded and set to missing. Missing data which will be multiply imputed using a control-based strategy as described in ([Section 5.3](#)). A thousand (1000) imputed datasets will be used in the analysis and results combined using PROC MIANALYZE.
- The least-squares (LS) means, the 90% confidence interval for the LS means, the difference between the LS means for each pair of treatment groups, and the corresponding 90% confidence interval will be presented.

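### The visible ANCOVA and MMRM leave out the randomisation stratum (IGA or PGA 2 vs 3): a minor efficiency and design-consistency point, with no effect on validity

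*SAP*

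**What the plan says.** Protocol 4.1 states: "Randomization will be stratified by baseline disease severity". The factor is IGA 2 vs 3 in AD and PGA 2 vs 3 in psoriasis. The mild share is capped in both indications; for AD, SAP 2.2 puts it as "Up to 25% of AD participants will have an IGA score of 2 at baseline".

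The analysis models do not carry that factor:

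- Protocol 9.4.1 (AD primary): "A landmark analysis using analysis of covariance of percent change from baseline in EASI, adjusting for the baseline EASI score".
- Protocol 9.4.2 (psoriasis primary): "A landmark analysis using analysis of covariance of change from baseline PASI, adjusting for the baseline PASI score".
- SAP 5.2.2 (general method): "The ANCOVA model will include terms for treatment arm and baseline score of the dependent variable".
- SAP 6.1.1.1 (primary analysis): an ANCOVA "with treatment arm and baseline EASI score as the independent variables", with the same method for PASI.
- SAP 6.2.3.1 (secondary continuous endpoints): treatment and the baseline value of the endpoint.
- SAP 5.2.2, 6.1.1.2 and Appendix 7 (MMRM): treatment, visit and their interaction. Baseline is missing from the list in 6.1.1.2 but is included in 5.2.2 and in the code.
- SAP 6.1.1.2 (ANOVA sensitivity analysis): neither baseline score nor stratum, by design.
- SAP Appendix 4 (code): baseline only in the imputation step, baseline and treatment in the analysis step.

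The only visible analysis remark on stratification factors is in the adverse-event section (SAP 6.7.1), which says they are not adjusted for. Some sections contain blacked-out text, so this point covers the visible models only.

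**The concern.** A factor used to balance the arms is normally carried into the model. Stratifying removes chance imbalance on severity, but a model without the factor leaves any stratum-related variation in the residual. The reported SE is then somewhat too large for the design that was run. The trial is small (21 and 12 expected completers per arm) and its primary results are presented with 90% confidence intervals, so cheap precision is worth having. What is at stake is the width of those intervals, not whether the estimates are right.

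**Working it through.** **Inputs from the documents** (Protocol 9.2.1, 9.2.2, 4.1)

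- AD: difference 50, SD 48, 28 randomised and 21 evaluable per arm, two-sided alpha 0.05.
- Psoriasis: difference 4.5, SD 4.2, 16 randomised and 12 evaluable per arm, two-sided alpha 0.10.
- Mild stratum: at most 25%.

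**Assumed, because the documents give no figure:** partial R² of the stratum given treatment and baseline score, taken as 0, 5, 10 and 20%. The stated SDs are treated as residual SDs after baseline score.

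**1. The plan's own power.** Two-sample t with noncentrality δ / (σ√(2/n)).

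- AD: 50 / (48 × √(2/21)) = 50 / 14.81 = 3.38, power 90.9% (stated about 90%).
- Psoriasis: 4.5 / (4.2 × √(2/12)) = 4.5 / 1.715 = 2.62, power 81.5% (stated about 80%).

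Both reproduce with no covariate, so the stated powers do not depend on the stratum.

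**2. What the assumed R² means.** Partial R² = p(1−p)(1−r²) × gap², with p = 0.25 and an assumed stratum–baseline correlation r = 0.4, so the multiplier is 0.1875 × 0.84 = 0.1575. The gap between strata is then √(R²/0.1575): 0.56 SD at 5%, 0.80 SD at 10% and 1.13 SD at 20%. The last equals 54 EASI percentage points or 4.7 PASI points, more than the planned drug effects, so 20% is an upper bound.

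**3. Completers, closed form.** Without the stratum, the 90% half-width is t(0.95, df) × σ√(2/n): 24.96 for AD (df 39) and 2.95 for psoriasis (df 21). With it, multiply by [t(0.95, df−1) / t(0.95, df)] × √(1−R²). The t ratio alone is 1.0006 (AD) and 1.0023 (psoriasis).

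| Partial R² | AD half-width | Psoriasis half-width |
|---|---|---|
| 0 | 24.97 (+0.1%) | 2.96 (+0.2%) |
| 5% | 24.34 (−2.5%) | 2.88 (−2.3%) |
| 10% | 23.69 (−5.1%) | 2.81 (−4.9%) |

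A completer simulation that allows for collinearity with baseline gave changes of +0.5, −2.2 and −4.8% (AD) and +1.2, −1.8 and −4.7% (psoriasis). So on completers the two-term interval is about 2–5% wider than it need be at R² 5–10%.

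**4. The planned imputed analysis.** Simulation with 10,000 replicates per cell and 200 imputations. Arms were balanced on stratum (7 of 28 or 4 of 16 mild) with random dropout to 21 and 12 per arm. The imputation regression on baseline was fitted on vehicle and applied to both arms, with Rubin pooling and the stratum in the analysis model only. Mean reported SE, without vs with the stratum:

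| Partial R² | AD SE | Excess without | Psoriasis SE | Excess without |
|---|---|---|---|---|
| 0 | 14.88 vs 14.91 | −0.2% | 1.789 vs 1.795 | −0.4% |
| 5% | 14.90 vs 14.77 | +0.9% | 1.790 vs 1.778 | +0.6% |
| 10% | 14.93 vs 14.64 | +2.0% | 1.794 vs 1.765 | +1.6% |
| 20% | 14.96 vs 14.34 | +4.3% | 1.799 vs 1.733 | +3.8% |

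(Percentages come from unrounded SEs.) At R² 10%, the 90% half-width goes from 24.6 to 24.1 (AD) and from 2.95 to 2.91 (psoriasis). The gain is smaller than on completers because imputed values carry no stratum effect beyond baseline. Two repeat simulations agreed within 0.2 percentage points.

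**5. Break-even**, interpolating between R² 0 and 5%: AD 5 × 0.2/1.1 ≈ 1%; psoriasis 5 × 0.4/1.0 = 2%.

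**6. Sensitivity.**

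- Lower dropout (3 of 28, 2 of 16 per arm): excess SE at R² 5% and 10% is +1.7 and +3.6% (AD), +1.4 and +3.0% (psoriasis).
- Fewer mild participants: a gap of 0.8 SD in AD gives +2.0% at 25% mild but +0.9% at 11% mild.
- Closer to Appendix 4 (raw EASI imputed within 0–72, then converted to percent change; assumed baseline distributions): AD excess 0.8–0.9% at a 0.56 SD gap and 1.4–1.9% at 0.8 SD.

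**7. Type I error.** In the completer simulation at nominal 0.10 and R² 10%, it is 0.088 without the stratum in both indications, against 0.101 with it. That is conservative, not inflated.

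**The case against.** The strongest reply is that the gain is small and hypothetical. The models already adjust for baseline EASI or PASI, which are finer severity measures than a two-level global score, and the AD endpoint is itself scaled to baseline. Nothing in the documents says the stratum adds information beyond that. This stands: confidence is high about the omission and only conditional about the benefit.

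Two further objections also stand. First, 25% is a cap, so the mild stratum may be sparse or empty and the term useless or inestimable; a rule for that case is needed. Second, the ANOVA in SAP 6.1.1.2 exists to show the effect of removing baseline, and a severity factor would defeat its purpose, so it should stay as it is.

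It can also be said that a term in the analysis model but not in the imputation model is awkward. That is fair, but the vehicle arm may be too thin to estimate it. With 4 of 16 mild and 4 random dropouts, the chance of fewer than 3 mild vehicle completers in psoriasis is 24%. For AD with 7 of 28 mild it is only 0.4%, so the reason is weaker there.

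A reader might infer more: that ignoring the stratification biases the estimate, invalidates the test or leaves the trial underpowered. The documents do not support this. Allocation is balanced within strata, the test is conservative without the term, and the power figures reproduce without it. Nor would the stratum bring the planned test to its nominal level. In the simulation, the reported SE with no stratum effect exceeds the true spread by about 34–35% with or without the term. That follows from pooling under control-based imputation and is a separate matter.

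**Conclusion.** The point holds as a minor one. The visible ANCOVA and MMRM omit a factor by which participants are randomised, without a stated reason. The cost is precision only: about 0.5–2% of the reported SE in the planned analysis at an assumed partial R² of 5–10%, and about 2–5% on completers. If the stratum adds nothing beyond baseline score, including it raises the SE by about 0.2–0.4%. These sizes rest on the assumed R², the mild stratum at its 25% cap, 25% random dropout and a stratum–baseline correlation of 0.4. The MMRM was not simulated; the completer figures are only a rough guide to it. The case for the change is matching the analysis to the design at very low cost, not correcting an error.

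**What to change.** Add the randomisation stratum (IGA 2 vs 3, PGA 2 vs 3) as a fixed factor in the ANCOVA and MMRM: Protocol 9.4.1 and 9.4.2; SAP 5.2.2, 6.1.1.1, 6.1.1.2 (MMRM only) and 6.2.3.1; and the code in Appendices 4 and 7. In Appendix 4 the stratum variable must also be kept in the data steps.

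State that LS means are computed at the observed stratum proportions. Equal weighting would give a stratum capped at 25% half the weight in the per-arm means; the treatment difference is unaffected.

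Prespecify that the term is dropped if either stratum is empty or too sparse in an arm, for example fewer than 2 participants per arm in the analysis.

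Leave unchanged the ANOVA sensitivity analysis and the Chan-Zhang analyses of responder endpoints. The imputation rule, under which the SAP will "impute missing treatment observations assuming they are similar to corresponding vehicle patients", can also stay as written; adding the stratum there is optional.

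The cost is one model degree of freedom, a variable already collected for randomisation, and a few lines of text. Protocol section 9 says that "any major modifications of the primary endpoint definitions or their analyses will also be reflected in a protocol amendment", and the SAP introduction says the same, so the sponsor must decide whether this counts as major. If the two-term model is preferred, one sentence giving the reason closes the point.
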